10.2.7 Outcome

- Recovered/resolved – subject returned to first assessment status with respect to the AE.
- Recovering/resolving – the intensity is lowered by one or more stages: the diagnosis has or signs/symptoms have almost disappeared; the abnormal laboratory value improved, but has not returned to the normal range or to the baseline value; the subject died from a cause other than the particular AE with the condition remaining “recovering/resolving.”
- Not recovered/not resolved – there is no change in the diagnosis, signs or symptoms; the intensity of the diagnosis, signs/symptoms or laboratory value on the last day of the observed study period has become worse than when it started; is an irreversible congenital anomaly; the subject died from another cause with the particular AE state remaining “Not recovered/not resolved.”

- Recovered/Resolved with sequelae – the subject recovered from an acute AE but was left with permanent/significant impairment (eg, recovered from a cardiovascular accident but with some persisting paresis).
- Fatal – an AE that is considered as the cause of death.
- Unknown – the course of the AE cannot be followed up due to hospital change or residence change at the end of the subject's participation in the study.

10.2.8 Collection and Reporting of AEs, SAEs, AESIs, and Abnormal LFTs

10.2.8.1 Collection Period

Collection of AEs (ie, AEs, SAEs, AESIs, and abnormal LFTs) will commence at the time the subject signs the informed consent. Routine collection of AEs will continue until approximately 30 days after the last dose of investigational product. For subjects who discontinue prior to the administration of study medication, AEs will be followed until the subject discontinues study participation.

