ⁱ Urine PK samples will be collected at the following time intervals: predose, 0-4, 4-7, 7-12, and 12-24 hours.

^j Immunogenicity serum samples for ADA testing will be taken at predose on Day 1, on Day 8, at ET (if applicable), and at follow-up visits on Day 14 and Day 29. If ADAs are present, subjects may be asked to return for additional sample collection. All subjects receiving either study drug or placebo will have the same collection time points.

^k If subjects have provided consent for the optional DNA collection, blood samples should be collected and can be collected at any time on the day of discharge or at ET (if applicable).

^m Subjects will be confined.

3.3 Part 3 for Dose Titration and Redosing Cohorts 18 to 20: Screening Through Day 15, Follow-Up, and Early Termination

3.3.1 Overall Schedule of Study Procedures for Part 3

Table 3.f Part 3 for Dose Titration and Redosing Cohorts 18 to 20: Screening Through Day 15, Follow-Up, and ET

	Days															ET		
	Screen	-28 to -3	-2 ^a	-1	Dosing							8 (Discharge)	9 to 13 Wash out ^b	Day 13 ±1 day (Confine again)	Day 14 ±1 day (Single Dose)	Day 15 ±1 day (Discharge)	Follow-up Visit Day 29 ±3 days	
					Pre dose	1	2	3	4	5	6							
Administrative Procedures																		
Informed consent	X																	
Inclusion/exclusion criteria	X	X			X													
Medical history/demographics	X																	
Prior and concomitant medications		X-----														X-----		
Clinic Procedures/Assessments																		
Full physical examination	X	X										X ^c		X		X ^c	X	
Height	X																	
Weight and BMI	X	X																
Vital signs ^d	X		X	X	X	X	X	X	X	X	X		X	X	X	X		
Standing BP and pulse ^e	X		X	X	X	X	X	X	X	X	X		X	X	X			
12-Lead ECGs	X	X			X							X		X		X		
ECG telemetry (12-lead)			X ^f		X-----	Continuous	-----	X						X				
Telemetry extraction ^g			X	X	X	X	X	X	X	X	X	X		X	X			

CONFIDENTIAL

Table 3.f Part 3 for Dose Titration and Redosing Cohorts 18 to 20: Screening Through Day 15, Follow-Up, and ET

	Days																ET	
	Screen	Dosing										8 (Dis-charge)	9 to 13 Wash out ^b	Day 13 ±1 day (Confine again)	Day 14 ±1 day (Single Dose)	Day 15 ±1 day (Dis-charge)	Follow-up Visit Day 29 ±3 days	
		-28 to -3	-2 ^a	-1	Pre dose	1	2	3	4	5	6							
TAK-510/placebo administration ^h					X	X	X	X	X	X	X				X			
AE monitoring	X	X	X-----Continuous-----X															
Laboratory Procedures/Assessments																		
Safety laboratory collection ⁱ	X		X	X	X	X		X		X	X			X	X	X	X	

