3.3.5 Part 3 Day 9 Through Day 15 Assessments, Follow-Up, and Early Termination

Table 3.j Part 3 Day 9 Through Day 15 Assessments, Follow-Up, and ET

	Days 9 to 13	Day 13	Scheduled Time														Follow-up Visit Day 29 ±3 days	ET
			Day 14 (Hours)															
	Washout ^a	Pre dose	0	0.5	1	2	3	4	5	7	10	12	16	24	30 (Discharge) (Day 15)			
Administrative Procedures																		
Previous and concomitant medications	X		X-----Continuous review-----X															
Clinic Procedures/Assessments																		
Full physical examination		X														X ^b	X	X
Weight and BMI ^c		X																
Temperature and respiratory rate		X	X				X		X							X		
BP and pulse ^c		X	X		X	X	X	X	X	X	X	X	X	X	X	X	X	X
Standing BP and pulse ^d		X	X		X		X		X		X	X			X	X		
12-lead ECGs		X														X		X
ECG telemetry (12-lead)			X-----Continuous monitoring-----X															
Telemetry extraction			X		X		X	X	X		X		X		X			
TAK-510/placebo administration			X															
AE monitoring	X		X-----Continuous review-----X															X
Laboratory Procedures/Assessments																		
Safety laboratory collection ^e		X	X													X	X	X
Serum sample for CK ^f																		X
Glucose finger stick			X					X										
Urine drug screen		X																
Alcohol breath test		X																
Cotinine test		X																
βhCG (pregnancy) test ^g		X																X

CONFIDENTIAL

Table 3.j Part 3 Day 9 Through Day 15 Assessments, Follow-Up, and ET

	Days 9 to 13	Day 13	Scheduled Time													ET	
			Day 14 (Hours)														
	Washout ^a	Pre dose	0	0.5	1	2	3	4	5	7	10	12	16	24	30 (Discharge) (Day 15)	Follow-up Visit Day 29 ±3 days	
PK Evaluations																	
Plasma sample for TAK-510 PK			X			X		X	X			X		X	X	X	
Immunogenicity and Biomarkers																	
Serum sample for immunogenicity ^b			X													X	X
Other																	
Confinement ^c			X-----X														

ADA: antidrug antibodies; AE: adverse event; anti-HCV: antibodies to hepatitis C virus; β hCG: beta human chorionic gonadotropin; BMI: body mass index; BP: blood pressure; CK: creatine kinase; ECG: electrocardiogram; ET: early termination; [REDACTED]; HBsAg: hepatitis B surface antigen; PK: pharmacokinetic.

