Optional DNA samples will also be collected from subjects that provide consent for collection through a separate procedure. DNA samples can be collected at any time on the day of discharge (Day 8) or at early termination (if applicable). Subjects will be discharged on Day 8 and will be readmitted the evening prior to redosing. After a 7-day washout (168 hours after the last dose of the 7-day treatment period), subjects will be dosed with a single dose of study drug (ie, at the same dose and double-blind treatment assignment as their highest daily dose during the 7-day treatment period). The duration of washout may be subject to change based on emerging safety, tolerability, and available PK data. Subjects will be confined the evening prior to redosing and for at least 30 hours after their redosing, while not being confined for the entire washout period. Subjects will return after discharge for additional immunogenicity and other assessments at follow-up visits on Day 29. Based on emerging safety, tolerability, and available PK data, subjects may be confined during washout at the discretion of the investigator in consultation with the sponsor and medical monitor.

In Part 3, up to 3 cohorts may be dosed sequentially for 7 days using a dose titration design of 1 to 5 days at lower doses followed by 2 to 6 days at the highest dose for that cohort, which will not exceed the dose studied in the highest completed dose cohort in Part 2. Cohorts 18 and 19 may be started in parallel. The proposed dose titration designs for the 3 cohorts are as follows:

Cohort 18: Single doses that escalate on a daily basis will be given on the first 2 to 5 days of the 7-day dosing period, followed by a maximum daily dose on the remaining days of the 7-day dosing period.

Cohort 19: A lower starting dose will be given on the first 2 to 3 days of the 7-day dosing period, followed by a maximum daily dose for the remaining days of the 7-day dosing period. The lower starting dose is to be determined based on Cohort 18.

Cohort 20: The initial daily dose(s) are to be determined by Cohorts 18 and 19 and will be given on the first 1 to 3 days, followed by the maximum daily dose for the remaining days of the 7-day dosing period. The maximum daily dose will be the same as that Cohorts 18 and 19, or higher as supported by safety, tolerability, and PK data from at least the same daily dose (or higher) in Part 2 MRD cohorts.

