9.3.3 Part 3 (Dose Titration and Redosing)

Subjects will report to the clinical site on Day -2. Subjects will remain in the clinic until discharge on Day 8, 30 hours after last dose of study drug. Based on emerging safety, tolerability, and available PK data, subjects may be confined during washout at the discretion of the investigator in consultation with the sponsor and medical monitor. Subjects will report to the clinical site for readmission on the evening before the scheduled day of study drug redosing (Day 13). Subjects will remain in the clinic until discharge on Day 15, 30 hours after the single dose of study drug on Day 14. At the discretion of the investigator, subjects may be requested to remain in the study site longer.

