10.2.8.2 Reporting AEs

At each study visit, the investigator will assess whether any subjective AEs have occurred. A neutral question, such as "How have you been feeling since your last visit?" may be asked. Subjects may report AEs occurring at any other time during the study. Subjects experiencing an SAE prior to the first exposure to investigational product must be monitored until the symptoms subside and any clinically relevant changes in laboratory values have returned to Baseline or there is a satisfactory explanation for the change. Nonserious AEs that begin prior to the first exposure to investigational product, related or unrelated to the study procedure, need not be followed-up for the purposes of the protocol.

All subjects experiencing AEs, whether considered associated with the use of the study medication or not, must be monitored until the symptoms subside and any clinically relevant changes in laboratory values have returned to Baseline or until there is a satisfactory explanation for the changes observed. All AEs will be documented in the AE page of the eCRF, whether or not the investigator concludes that the event is related to the drug treatment. The following information will be documented for each event:

- Event term.
- Start and end date and time.
- Pattern of AE (frequency).
- Severity/Intensity.
- Causality (Investigator's opinion of the causal relationship between the event and administration of study drug).
- Action taken with study drug.

- Outcome of event.
- Seriousness.

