10.2.8.3 Reporting SAEs

When an SAE occurs through the AE collection period it should be reported according to the procedure outlined below:

A Takeda SAE form must be completed, in English and signed by the investigator immediately or within 24 hours of first onset or notification of the event. The information should be completed as fully as possible but contain, at a minimum:

- A short description of the event and the reason why the event is categorized as serious.
- Subject identification number.
- Investigator's name.
- Name of the study medication(s).
- Causality assessment.

The SAE form should be transmitted within 24 hours to the attention of the contact listed in Section 14.1.1.

Any SAE spontaneously reported to the investigator following the AE collection period should be reported to the sponsor if considered related to study participation.

Reporting of SAEs that begin before first administration of investigational product will follow the same procedure for SAEs occurring on treatment.

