11.1.4.1 AEs

The summary of treatment-emergent adverse events (TEAEs) will include the number and percentage of subjects with at least 1 TEAE by MedDRA System Organ Class and Preferred Term and by placebo, each TAK-510 dose level (Parts 1 and 2 only)/dose regimen (Part 3), and TAK-510 overall within each part of the study separately. Similar summary analyses will be provided for treatment-related TEAEs, SAEs, AESIs, and AEs leading to permanent treatment discontinuation as well. For Part 3 only, similar summary analyses of TEAEs will be performed for the single dose after 7 days of washout from multiple dose regimens of TAK-510 by placebo, TAK-510 single dose level after washout, and TAK-510 single dose overall after washout.

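### Part 3 schedules no contact beyond about 15 days after the redose, although the protocol sets adverse event collection at about 30 days after the last dose

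*Protocol*

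**What the plan says.** Section 10.2.8.1 covers AEs, SAEs, AESIs and abnormal LFTs together and does not distinguish between parts: "Routine collection of AEs will continue until approximately 30 days after the last dose of investigational product".

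In Part 3 the last dose is the single redose after washout. Its column heading in Table 3.f (Section 3.3.1) begins "Day 14 ±1 day (Single Dose". Section 9.3.3 keeps subjects in the clinic until "30 hours after the single dose of study drug on Day 14". The only later column, apart from early termination, is "Follow-up Visit Day 29 ±3 days" (Tables 3.f and 3.j). Section 6.1.4 agrees: "Subjects will return after discharge for additional immunogenicity and other assessments at follow-up visits on Day 29". The Study Summary (Section 1.0) also ends participation at Day 29, for a planned duration of about 57 days from Day -28.

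On how events are found, Section 10.2.8.2 says: "At each study visit, the investigator will assess whether any subjective AEs have occurred". It also allows subjects to report events at other times during the study. Section 10.2.8.3 ties SAE reporting to the same period: "When an SAE occurs through the AE collection period it should be reported according to the procedure outlined below". After that period, only spontaneously reported SAEs considered related to study participation go to the sponsor.

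Section 11.1.4.1 plans a separate output for the redose: "For Part 3 only, similar summary analyses of TEAEs will be performed for the single dose after 7 days of washout".

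**The concern.** A collection period is only as good as the contacts that support it. Section 10.2.8.1 looks like a general sentence that fits a single dose on Day 1 with a last visit at Day 29. It appears not to have been adapted to Part 3, where the last dose comes two weeks into the study and the last visit stays at Day 29. Active questioning happens at visits, and no visit or call is scheduled later.

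Adverse events are one component of the primary safety and tolerability endpoint (Section 5.2.1). Safety after the redose is a Part 3 secondary objective (Section 5.1.2) with its own TEAE summary. If the schedule stops halfway through the stated period, a reader of that summary could assume 30 days of elicited follow-up when there are about 15. Part 3 is also meant to be compared descriptively with Parts 1 and 2 (Section 6.1.4), where scheduled follow-up after the last dose is longer. Section 10.2.8.1 also includes abnormal LFTs. A subject cannot report a symptomless laboratory change, and no laboratory test is scheduled after Day 29.

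**Working it through.** **Inputs**
- Collection period: about 30 days after the last dose (Section 10.2.8.1).
- Last dose: Day 1 in Part 1 (Table 3.a), Day 5 in Part 2 (Section 6.1.3, Table 3.b), Day 14 ±1 in Part 3 (Table 3.f).
- Last scheduled visit: Day 29 ±3 in every part (Tables 3.a, 3.b and 3.e, 3.f and 3.j).
- Part 3 size: up to 24 subjects, 6 TAK-510 and 2 placebo per cohort (Section 6.1.4, Table 6.a).

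**The plan's own figures reproduce.** With no Day 0, Day -28 to Day 29 is 28 + 29 = 57 days, as stated. Day 7 to Day 14 is 7 × 24 = 168 hours, the stated washout.

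**Gap from last dose to last scheduled visit.** Nominal gap = visit day − dose day. Shortest gap = earliest visit − latest dose. Longest gap = latest visit − earliest dose.

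| Part | Nominal | Shortest | Longest | Last dose + 30 |
|---|---|---|---|---|
| 1 | 29 − 1 = 28 | 26 − 1 = 25 | 32 − 1 = 31 | Day 31 |
| 2 | 29 − 5 = 24 | 26 − 5 = 21 | 32 − 5 = 27 | Day 35 |
| 3 | 29 − 14 = 15 | 26 − 15 = 11 | 32 − 13 = 19 | Day 44 |

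**Part of the 30 days after the last scheduled contact**
- Part 3: 30 − 15 = 15 days (30 − 19 = 11 to 30 − 11 = 19).
- Part 2: 30 − 24 = 6 days (30 − 27 = 3 to 30 − 21 = 9).
- Part 1: 30 − 28 = 2 days nominally, and the visit window reaches Day 32, past Day 31.

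**Can the windows close the Part 3 gap?** The latest permitted visit is Day 32. From a Day 14 redose the shortfall is 44 − 32 = 12 days. From the earliest redose, Day 13, it is 43 − 32 = 11 days. No permitted combination reaches 30 days.

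**Subjects affected.** Up to 24 in Part 3, of whom 24 × 6/8 = 18 receive TAK-510.

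**Is a later contact scheduled anywhere?** Section 6.5.2 says the last interaction may be by phone, but it only defines the end of the study and schedules no call. If the last subject is in Part 3 and is seen at Day 29, the study ends about 15 days before that subject's collection period does. Recall of ADA-positive subjects (Table 3.j footnote) is conditional and is not an adverse event contact.

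**The case against.** The strongest reply is that collecting events does not require a visit. Section 10.2.8.2 lets subjects report at any time during the study and requires known events to be followed until they subside or are explained. Section 10.2.8.3 still captures later related SAEs that are reported spontaneously. The cardiovascular effects that motivate Part 3 (Section 6.3.2.5) are expected early and are watched in-house for 30 hours. Both arms follow one schedule, so the gap does not differ between TAK-510 and placebo within Part 3. No formal inference is planned. All of this stands and limits the harm, but none of it supplies a scheduled contact after Day 29.

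A second reply is that the protocol states no attribution window for the redose TEAE summary, and the SAP may end it at Day 29. That is fair, and the protocol does not make 30 days the window for that table. It does not remove the conflict, because elicited follow-up after the redose is about 15 days whatever window is chosen, and an SAP cannot create a contact.

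Third, the 30 days are stated as approximate. That covers Part 1 and may cover Part 2, so Part 2 is not counted here as an error. It cannot stretch 15 days to 30.

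Fourth, the 11 to 19 day range takes the dosing and visit windows at opposite extremes, and Table 3.j shows no ±1 day on the Day 14 dose. The nominal 15 days carries the point without the range.

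Finally, the Part 3 primary objective concerns the titration regimen. Counted from the Day 7 dose that ends it, the Day 29 visit is 29 − 7 = 22 days out. The full shortfall concerns the redose.

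**Conclusion.** The concern holds. For Part 3 the stated collection period and the visit schedule disagree: about 30 days against 15 scheduled (11 to 19 with windows). Roughly the second half of the period has no planned contact for up to 24 subjects.

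This should be fixed, but it does not threaten the study. Acute effects after the redose are captured, known events are followed, and the SAE reporting rule exists. What is lost is prompted detection of new events, and any laboratory detection, late in the stated period.

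The figures assume that the redose is given, that the dosing and visit windows vary independently, and that the last visit stays at Day 29. The protocol allows the washout to be shortened or lengthened in Cohorts 19 and 20. If it is lengthened and the visit does not move, the gap between redose and last contact becomes shorter still.

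**What to change.** Reconcile Section 10.2.8.1 with Tables 3.f and 3.j and with the 57-day duration in Section 1.0, in one of two ways:

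- **Add a contact.** Schedule a final adverse event contact in Part 3, timed from the last dose rather than from Day 1. A phone call is enough to elicit events. At 30 days after the redose, the stated Part 3 duration becomes 28 + 44 = 72 days. If the sponsor does not accept 24 days as approximately 30, add the same contact in Part 2 (28 + 35 = 63 days) and amend Tables 3.b and 3.e.
- **Restate the period.** Give, by part, the collection period that the schedule actually delivers.

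Either way, Section 10.2.8.3 should use the same end date. The text should also say whether abnormal LFTs share it, since a phone call cannot detect them.

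The cost is protocol wording only, or wording plus one call for each of up to 24 Part 3 subjects, with up to 64 more calls only if Part 2 is included.

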10.2.8.2 Reporting AEs

At each study visit, the investigator will assess whether any subjective AEs have occurred. A neutral question, such as "How have you been feeling since your last visit?" may be asked. Subjects may report AEs occurring at any other time during the study. Subjects experiencing an SAE prior to the first exposure to investigational product must be monitored until the symptoms subside and any clinically relevant changes in laboratory values have returned to Baseline or there is a satisfactory explanation for the change. Nonserious AEs that begin prior to the first exposure to investigational product, related or unrelated to the study procedure, need not be followed-up for the purposes of the protocol.

All subjects experiencing AEs, whether considered associated with the use of the study medication or not, must be monitored until the symptoms subside and any clinically relevant changes in laboratory values have returned to Baseline or until there is a satisfactory explanation for the changes observed. All AEs will be documented in the AE page of the eCRF, whether or not the investigator concludes that the event is related to the drug treatment. The following information will be documented for each event:

- Event term.
- Start and end date and time.
- Pattern of AE (frequency).
- Severity/Intensity.
- Causality (Investigator's opinion of the causal relationship between the event and administration of study drug).
- Action taken with study drug.

- Outcome of event.
- Seriousness.

10.2.8.3 Reporting SAEs

When an SAE occurs through the AE collection period it should be reported according to the procedure outlined below:

A Takeda SAE form must be completed, in English and signed by the investigator immediately or within 24 hours of first onset or notification of the event. The information should be completed as fully as possible but contain, at a minimum:

- A short description of the event and the reason why the event is categorized as serious.
- Subject identification number.
- Investigator's name.
- Name of the study medication(s).
- Causality assessment.

The SAE form should be transmitted within 24 hours to the attention of the contact listed in Section 14.1.1.

Any SAE spontaneously reported to the investigator following the AE collection period should be reported to the sponsor if considered related to study participation.

Reporting of SAEs that begin before first administration of investigational product will follow the same procedure for SAEs occurring on treatment.

10.2.8.3.1 SAE Follow-Up

If information is not available at the time of the first report becomes available at a later date, the investigator should complete a follow-up SAE form or provide other written documentation and fax it immediately within 24 hours of receipt. The site must use the eCRF to report an SAE within 24 hours, and, only if the eCRF is unavailable, should the site send a safety reporting form. Copies of any relevant data from the hospital notes (eg, ECGs, laboratory tests, discharge summary, postmortem results) should be sent to the addressee, if requested.

All SAEs should be followed up until resolution or permanent outcome of the event. The timelines and procedure for follow-up reports are the same as those for the initial report.

